Study Background and Rationale: Among patients receiving opioids for noncancer pain, recent research in North America showed a strong association between doses and opioid-related mortality, especially at dosages exceeding thresholds recommended in recent guidelines. However, the focus on over-dosage may underestimate overall opioid-related mortality and data on death associated with opioid use in a population-based cohort of chronic noncancer pain patients in Europe is scarce. Especially comparative studies studying the safety of long-term opioid therapy in a real-world setting relative to non-opioid medication for chronic noncancer pain are needed in a European context.

Research Question and Objective(s): The primary objective is to investigate the association between mortality among patients with chronic noncancer pain with long-term opioid-therapy compared to non-opioid pain medication. The secondary objectives are to determine the risk of addiction/abuse and hospital admissions among opioid users with chronic non-cancer pain compared to patients with non-opioid pain medication.

Study Design/Type: This is a cross-sectional observational cohort study between 2012 and 2017 of patients with chronic noncancer pain.

Study Population and Data Resource: The data will be retrieved from an anonymized German health claims database including 4,00,000 persons insured by 69 German statutory health insurances. The data set includes 5.0% of the population covered by statutory health insurances

from January 1, 2012, to December 31, 2017. Only anonymized and aggregated data (no directly or indirectly identifying data) will be extracted.

Summary of Patient Eligibility Criteria: From the data extraction, the cohort will be analysed according to the following criteria:

Inclusion criteria: At least one diagnosis of pain R51 (headache), R52* (pain, not elsewhere classified), M00 – M99 (Diseases of the musculoskeletal system and connective tissue), G43* (migraine), G44* (other headache syndromes), G50.0 (trigeminal neuralgia), G50.1 (atypical facial pain), F45.4* (persistent somatoform pain disorder), G62* (polyneuropathies), E10.4*-E14.4 plus G63.3 (diabetes mellitus with neurological complications) in at least 3 quarters between 01.01.2012 and their first opioid claim AND opioid medication (Cohort A) OR non-opioid medication (Cohort B) between 01.01.2012 and first pain medication claim.

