8.2 Secondary objectives

In addition, present study aims to determine the risk of addiction/ abuse and hospital admissions among opioid users with chronic non-cancer pain compared to patients with non-opioid pain medication.

The secondary objectives will be addressed with following hypotheses:

- How often do patients on long-term opioid therapy and patients with non-opioid pain medication being hospitalized and how long do they stay in hospital?
- Does the number of hospitalizations and length of stay in hospital differ between patients on long-term opioid therapy compared to patients with non-opioid pain medication in time period of five years?
- How many misuse and addiction diagnoses were coded in outpatient sector for patients on long-term opioid therapy and patients with non-opioid pain medication in time period of five years?
- Does the number of outpatient misuse and addiction diagnoses differ between patients on long-term opioid therapy compared to patients with non-opioid pain medication in time period of five years?
- How many sick leave days do patients on long-term opioid therapy and patients with non-opioid pain medication have in time period of five years?

9. Research Methods

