9.2.1 Study Period

Due to data protection regulations in Germany, only an extract of maximum 6 years of data coverage could be available for the research purposes: 1st January 2012 to 31st December 2017.

The **baseline period** is defined as the period prior to the date of first diagnosis of diagnoses or first opioid or non-opioid treatment initiation as described in inclusion criteria (Chapter 9.2.2.1). The baseline assessment period endures between January 01, 2012 and first study medication prescription.

Index treatment is defined as the date of first opioid or non-opioid treatment prescription between 1st January 2013 and 31st December 2017.

Exposure time is defined as time between index treatment and December 31, 2017. Considering data availability of a maximum of 6 years and prescription in a required time period of 60 months, exposure time endures maximum five years. Thus, patients can be censored at death (death date in the linked records), last known record for the patient in the German health claims database, switching of treatment groups (from opioid group to non-opioid group or vice versa), 12 months without opioid/non-opioid treatment or 31st December 2017 (end of latest data cut), whichever comes first.

[figure not shown]
The **outcomes** will be assessed between index treatment and 31.12.2017.

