9.2.2.2 Exclusion Criteria

Following exclusion criteria will be used to extract the eligible study population (see also Figure 2):

Cohort A and B:

- Patients with present opioid and non-opioid pain medication prescriptions in 2012 are excluded from analysis (therapy-naïve patients only).
- Cancer patients will be excluded if the cancer diagnosis is accompanied by at least one of the following treatments in the same quarter: radiation therapy or chemotherapy all defined by the codes in Table 9-3. Diagnoses will be assessed via ICD-10 diagnoses during the inclusion period from 1 January 2012 until index treatment and main and secondary hospital diagnoses (i.e. *Haupt- und Nebendiagnosen*) will be taken into account.
- Palliative care, coded by ICD-10 code Z51.5 or OPS code 8-982*, 8-98e*, 8-98h* before index date is excluded
- Opioid substitution treatment with ICD-10 code Z51.83 in the study period is excluded.

Table 9-3: Exclusion criteria for cancer patients

Name	ICD-10 Code	
Malignant neoplasms	C00-C97	
Plus at least one the following in the same quarter		
Name	Code	Type of Code
Palliative care	Z51.5	ICD-10
Chemo therapy	Z51.1	ICD-10
Radiation therapy	Z51.0	ICD-10
Chemo therapy	8-541* 8-542* 8-543* 8-544* 8-546*	OPS Code

Radiation therapy	8-52*	OPS Code
Palliative care	8-982* 8-98e* 8-98h*	OPS Code

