9.4.2.2 Secondary endpoints

Secondary endpoints are following:

- **Hospitalization due to any course.** Hospitalization will be assessed via the number of hospitalisations (calculated by counting the number of discharge dates (KH_Fall. Entlassungsdatum) in the year of interest, hospitalization rate, and length of stay in the hospital (KH_Fall. Verweildauer). The rate of hospitalization will be estimated as the number of patients with at least one hospitalization during the follow-up period divided by person-time of follow-up, censoring at time of death, last known record for the patient in the database, or 31st December 2017 (end of latest data cut), whichever is earlier.
- **Intensive care unit (ICU-stay)** stay is defined as patient's stay based on specialty of department in hospital (KH_OPS.Fachabteilung = 3600).
- **Hospitalization with to misuse or addiction.** The hospitalization with misuse or addiction will be analysed, if principal (main) diagnosis at discharge date between January 1st 2013 and December 31st 2017 contains at least one ICD-10 diagnosis of misuse/addiction: F10* or F11* or F13* or F19* or T40* (see also Appendix B in **Fehler! Verweisquelle konnte nicht gefunden werden.**).
- **Hospital admission diagnoses.** We report the hospital admission diagnoses based on ICD-10 codes between January 1st 2013 and December 31st 2017.
- **Coding of procedures in hospitals** that indicate number of patients that were hospitalized with severe diseases such as cardiovascular

diseases will be assessed via OPS-Codes provided in Appendix B as an excelsheet.

- **Coding of a misuse or addiction diagnosis in the outpatient sector** will be assessed via number of codings of misuse/addiction (ICD Codes = F10* or F11* or F13* or F19* or T40*) in outpatient sector by general practitioner or a specialist (e.g. psychiatrist), as ensured diagnosis (Diagnosesicherheit='G'). Additionally, the number of patients with a least one coding of ICD 10 codes of an ensured misuse/addiction in outpatient sector by general practitioner or a specialist (e.g. psychiatrist) will be assessed.
- **Sick leave** will be assessed as an absolute number and relative frequencies of patients with an attest of inability to work (patients with attest of inability to work as a percentage of all patients) in 2013-2017 and number of days being off work.
- **Hospital deaths** will be assessed via reason of discharge = death (Entlassgrund = Tod)

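### The outpatient misuse/addiction endpoint mixes diagnoses that existed before treatment with new ones, although the objective is the risk of addiction or abuse

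*Protocol*

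**What the plan says.** The protocol's opening summary and Section 8.2 give the aim in almost the same terms; Section 8.2 wants to "determine the risk of addiction/ abuse and hospital admissions among opioid users" relative to patients on non-opioid medication. Section 8.2 then turns this into a comparison of counts: "Does the number of outpatient misuse and addiction diagnoses differ between patients on long-term opioid therapy" and the non-opioid cohort over five years.

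Section 9.4.2.2 fixes the outpatient endpoint in detail: the code list, the diagnostic certainty flag and the sector. The outcome "will be assessed via number of codings of misuse/addiction", and additionally "the number of patients with a least one coding of ICD 10 codes of an ensured misuse/addiction in outpatient sector" is reported.

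Section 9.2.1 says that outcomes "will be assessed between index treatment and 31.12.2017". The same section starts the baseline period on 1 January 2012 and places the index prescription no earlier than 1 January 2013.

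The only addiction-related exclusion is in Section 9.2.2.2: "Opioid substitution treatment with ICD-10 code Z51.83 in the study period is excluded". The therapy-naïve requirement there concerns pain medication, not earlier misuse diagnoses.

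In Section 9.4.2.2 the hospital misuse endpoint is tied to calendar dates: "principal (main) diagnosis at discharge date between January 1st 2013 and December 31st 2017".

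**The concern.** Comparing the risk of addiction or abuse under two treatments needs cases that arise under those treatments. As written, a patient with an alcohol-dependence code in 2012 that is documented again after index counts as an outcome in whichever cohort the patient belongs to. Patients with several coded quarters add several units to the count of codings.

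The group difference is to be tested (Section 9.7.1 names chi-square and t-tests at 5%), so the number would be read as a treatment contrast. What is at stake is how that contrast is interpreted: a ratio of prevalent plus new cases may understate, overstate or reverse the ratio of new cases, depending on how many prior diagnoses each cohort carries.

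**Working it through.** **Plan's own figure.** None. The protocol gives no misuse rate, prior prevalence or cohort size, so every rate below is an assumption.

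**Formula.** Let b be the share of a cohort with a listed code before index, c the probability that such a patient is coded again after index, and i the risk of a new case among the rest. The share of patients with at least one code is

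p = b·c + (1 − b)·i

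**Balanced prior diagnoses.** Assume i = 1.0% (opioid) and 0.5% (non-opioid), a true ratio of 2.0, with the same b in both cohorts.

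| b | c = 1: opioid / non-opioid | ratio | c = 0.5: opioid / non-opioid | ratio |
|---|---|---|---|---|
| 1% | 1.990% / 1.495% | 1.33 | 1.490% / 0.995% | 1.50 |
| 3% | 3.970% / 3.485% | 1.14 | 2.470% / 1.985% | 1.24 |
| 5% | 5.950% / 5.475% | 1.09 | 3.450% / 2.975% | 1.16 |

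Dropping the small factor (1 − b) changes little: with c = 0.5 the 3% and 5% rows become 0.025/0.020 = 1.25 and 0.035/0.030 = 1.17.

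The absolute difference is (1 − b) × 0.5 percentage points, that is 0.495, 0.485 and 0.475. Dilution acts on the ratio and on precision, and hardly at all on the risk difference.

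**Precision.** Assume i = 2% versus 1%, c = 1, a two-sided 5% test (the protocol does not state sidedness) and 80% power.

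- No prior cases (b = 0): 2,319 patients per cohort.
- b = 3%: 7,101 per cohort; observed ratio 1.24.
- b = 5%: 10,457 per cohort; observed ratio 1.16.
- With 2,319 per cohort, power falls from 80% to 36% at b = 3% and to 26% at b = 5%.

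Restricting to code-free patients would instead need 2,319/0.97 = 2,391 per cohort before restriction at b = 3%, and 2,319/0.95 = 2,442 at b = 5%.

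**Unbalanced prior diagnoses.** Same 2% versus 1%, c = 1.

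- Opioid 3%, non-opioid 4%: 4.94% / 4.96% = 1.00.
- Opioid 3%, non-opioid 5%: 4.94% / 5.95% = 0.83.
- Opioid 5%, non-opioid 3%: 6.90% / 3.97% = 1.74.
- Opioid 3%, non-opioid 1%: 4.94% / 1.99% = 2.48.

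The true ratio is 2.0 in all four.

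**Count of codings.** Suppose a prior case is coded in twice as many quarters as a new one, with the 2% versus 1% rates. At b = 3% the ratio of counts is (0.06 + 0.0194)/(0.06 + 0.0097) = 1.14, and prior cases supply 0.06/0.0697 = 86% of non-opioid codings. The factor of two is an assumption.

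**The case against.** **The endpoint answers a question the protocol asks.** Section 8.2 asks how many misuse diagnoses were coded and whether the number differs, and Section 9.4.2.2 counts exactly that. This stands as a reason to keep the count. It does not settle the matter, because the sub-question is offered as the way to address a risk objective.

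**Matching could balance prior misuse.** Section 9.3.1 names sleep apnoea, depression and other comorbidities and refers to Appendix A, which is not shown, so it cannot be judged whether prior misuse is a covariate. Balance would remove confounding by prior misuse, which is a real gain. It would not remove the pull of the ratio towards 1.

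**Relapse is part of the risk too.** Restricting to code-free patients takes worsening or relapse out of the comparison. This stands and is a cost of the change.

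**Stronger readings that a reader might infer, and that the documents do not support:**

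- That the hospital endpoint counts admissions before index because its dates start on 1 January 2013. Section 9.2.1 starts all outcomes at index and Section 9.4.2 places them in follow-up, so this is an inconsistency of wording. The hospital endpoint also needs a principal discharge diagnosis, so each hit is an actual admission, and the argument about carried-over codes applies to it much less.
- That old diagnoses are re-coded every quarter and dominate the count. Section 9.2 says only that the quarter of documentation is recorded.
- That the endpoint is certain to hide a difference. Attenuation towards 1 holds only under balance, the absolute difference is then almost unchanged, and with no cohort size stated a very large sample could still detect it.

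**Conclusion.** The point holds for the outpatient misuse/addiction endpoint. Followed as written, the plan mixes existing with new cases while its objective is a risk compared between cohorts.

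The direction of the error depends on balance: towards a ratio of 1, with lost precision, if prior diagnoses are equal; either way if they are not. The size cannot be fixed from the documents. Under the assumed 1.0% versus 0.5%, balanced prior prevalence of 1% to 5% turns a true ratio of 2.0 into 1.33 to 1.09 with full re-coding, or 1.50 to 1.16 with half re-coding. These figures illustrate the mechanism and are not estimates for this database. The endpoint is secondary, and the primary mortality comparison is unaffected.

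**What to change.** For the comparison between cohorts, define the outcome as the first ensured outpatient code from the listed groups between index and censoring, among patients with none of these codes from 1 January 2012 to index who were insured throughout that look-back. Analyse it as time to first code. The protocol states no continuous-insurance criterion, so this one has to be added; Section 9.2 lists insurance start and end dates among the available data.

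Two details need a rule. Outpatient diagnoses are dated only by quarter, so a code in the index quarter cannot be placed before or after index; treating it as baseline is the cautious choice. Removing patients after matching breaks pairs, so either restrict before matching for this endpoint or re-check covariate balance in the restricted set.

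Keep the total number of codings and the count of all patients with at least one code as descriptive results. State the hospital misuse window as index to censoring, so that it agrees with Section 9.2.1.

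The cost is small: one more filter on data already in the extract. The downside is fewer patients and events, and relapse in patients with prior misuse will be visible only in the descriptive results.

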9.7.1 Planned Analyses

To address the main research questions, descriptive analyses, Cox proportional hazards regression and test for examining group differences (T-test and Chi² test) will be provided.

Descriptive analyses using mean, median, standard deviation, absolute and relative frequency, minimum and maximum will be reported.

To address the research questions about the differences between opioid and non-opioid treatment, inductive analyses using Chi² Tests and t-test with critical value at the 5% significance level will be employed.

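### The misuse/addiction endpoints pool alcohol, sedative, other-substance and all T40 codes with opioid disorders and plan no split, so a null result could not be read as no added opioid addiction risk

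*Protocol*

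**What the plan says.** Section 8.2 sets the secondary objective: the "present study aims to determine the risk of addiction/ abuse and hospital admissions among opioid users with chronic non-cancer pain", set against patients on non-opioid pain medication. One of its research questions is: "Does the number of outpatient misuse and addiction diagnoses differ between patients on long-term opioid therapy compared to patients with non-opioid pain medication". Neither sentence is limited to addiction to opioids.

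Section 9.4.2.2 turns this into two endpoints built on one code list.

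- **Hospital.** The endpoint is met when the principal discharge diagnosis "contains at least one ICD-10 diagnosis of misuse/addiction: F10* or F11* or F13* or F19* or T40" (all subcodes).
- **Outpatient.** The list is the same: "ICD Codes = F10* or F11* or F13* or F19* or T40*) in outpatient sector by general practitioner or a specialist". It is counted as the number of codings and also as "the number of patients with a least one coding of ICD 10 codes of an ensured misuse/addiction in outpatient sector".

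No result for F11 alone, and no breakdown by substance, is planned for either endpoint. For group differences, section 9.7.1 states that "inductive analyses using Chi² Tests and t-test with critical value at the 5% significance level will be employed".

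Three other places bear on the point. Section 9.2.2.2 excludes opioid substitution but not earlier alcohol or other substance diagnoses. Section 9.3.1 names depression among the propensity covariates and refers to Appendix A, which is not shown, for the rest. Sections 9.1 and 9.2.1 end follow-up when a patient switches between the two treatment groups.

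**The concern.** The study is motivated by the safety of long-term opioid therapy relative to non-opioid medication (section 7.2). A reader of its misuse result will want to know whether opioids add to addiction risk. Under the pooled list, an alcohol diagnosis in either cohort scores exactly as a new opioid dependence does. If many of the events are unrelated to which pain drug was prescribed, they add a common background to both cohorts. That background pulls the ratio towards 1 and adds noise to the test.

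Two features add to this. Because earlier substance diagnoses are not excluded, a long-standing alcohol disorder that is coded again during follow-up counts as an event. And because the outpatient endpoint also counts codings, and section 9.2 says outpatient diagnoses are documented by quarter, a chronic condition coded once a quarter for 60 months contributes 60/3 = 20 codings, against one for a patient with a single opioid code.

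At stake is the interpretation of a small or null pooled difference. It could be taken as evidence that opioids carry no added addiction risk, when the endpoint cannot separate that from dilution.

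**Working it through.** The protocol gives no event rate, effect size or sample size for these endpoints, so there is no figure of its own to reproduce. All rates below are assumptions, chosen to show a range. The substance labels are the ICD-10 titles; section 9.4.2.2 gives only the codes.

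**Step 1: dilution of the ratio.** Let f1 and f0 be the opioid-disorder risks in Cohorts A and B, and a the share with an alcohol code, equal in both cohorts and not overlapping with the opioid events.

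Pooled ratio = (a + f1)/(a + f0)

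| a | f1 = 1.5%, f0 = 0.5% (true ratio 3.0) | f1 = 1.0%, f0 = 0.5% (true ratio 2.0) |
|---|---|---|
| 1% | 2.5/1.5 = 1.67 | 2.0/1.5 = 1.33 |
| 2% | 3.5/2.5 = 1.40 | 3.0/2.5 = 1.20 |
| 4% | 5.5/4.5 = 1.22 | 5.0/4.5 = 1.11 |

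The risk difference does not shrink in this set-up: it stays at 1.0 or 0.5 percentage points. The ratio falls, and so does the ability to detect the difference, as step 2 shows.

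**Step 2: loss of power.** Take f1 = 1.0% and f0 = 0.5%, and a risk q of any other-substance code that is equal in both cohorts and independent of the opioid codes. Then pooled risk = 1 − (1 − f)(1 − q). For q = 2%, Cohort A has 1 − 0.99 × 0.98 = 2.98%, Cohort B has 1 − 0.995 × 0.98 = 2.49%, and the ratio is 1.20. The number per arm for 80% power, with 1:1 allocation and two-sided 5% (section 9.7.1 states the 5% but not the sidedness), is

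n = [1.96 × √(2p̄(1 − p̄)) + 0.8416 × √(p1(1 − p1) + p0(1 − p0))]² / (p1 − p0)², where p1 and p0 are the two risks compared and p̄ is their mean.

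| q | pooled ratio | n per arm for 80% | power at an assumed 10,000 per arm |
|---|---|---|---|
| none (opioid codes only) | 2.00 | 4,673 | 98.4% |
| 0.5% | 1.50 | 7,805 | 88.7% |
| 1% | 1.33 | 10,968 | 76.3% |
| 2% | 1.20 | 17,392 | 56.5% |
| 4% | 1.11 | 30,640 | 36.0% |
| 8% | 1.05 | 58,865 | 21.0% |

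**Step 3: what a reversal would need.** Balanced codes cannot change the direction. In the model of step 1, the sign flips only if alcohol codes are commoner in Cohort B by more than f1 − f0, that is by more than 1.0 point (true ratio 3.0) or 0.5 point (true ratio 2.0). For example, 1% in A and 3% in B gives (1.0 + 1.5)/(3.0 + 0.5) = 0.71. In the model of step 2, the A-to-B ratio of other-substance codes would have to be below about 0.50, 0.75, 0.88 or 0.94 at a Cohort B risk of 1%, 2%, 4% or 8%; at 0.5% no reversal is possible. The protocol has no data on any such imbalance.

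**The case against.** **The objective is general.** Section 8.2 speaks of addiction and abuse, not of opioid addiction, and a list covering several substances matches that wording. This stands: the pooled endpoint does not contradict the protocol and need not be replaced.

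**An opioid-specific endpoint has its own weakness.** Cohort B patients had no opioid prescription in 2012 and are censored on switching to opioids. F11 and opioid-poisoning codes will be rare there almost by design, whereas the broad list gives both cohorts a real chance of an event. This stands too. It is a reason to add the opioid-specific comparison next to the pooled one, not to substitute it.

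**A breakdown may come elsewhere.** An analysis plan may tabulate components, the hospital definition points to Appendix B through a broken cross-reference, and section 9.4.2.2 separately reports hospital admission diagnoses. This stands in part. The admission listing does not define the misuse endpoint, and there is no outpatient counterpart. The protocol itself fixes the code list, so the opioid-specific comparison belongs beside it.

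**Tempting stronger reading.** Cohort B includes antidepressant users, so a reader might infer that alcohol codes gather there and that the pooled result would turn in favour of opioids. The documents do not support this. They give no rates, depression is a named propensity covariate, and whether earlier substance disorder is among the remaining covariates cannot be judged without Appendix A. Nor can it be said that the endpoint measures mainly alcohol: with 1% alcohol codes an assumed ratio of 3.0 still shows as 1.67.

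**Conclusion.** The concern holds as one of interpretability. Both misuse/addiction endpoints merge opioid disorders with codes that may be unrelated to the study treatment, and no split is planned. A null pooled result therefore could not be read as no added opioid addiction risk, and a positive one could not be attributed to opioids. Under the assumed rates, a true ratio of 3.0 shows as 1.67 to 1.22, and one of 2.0 as 1.33 to 1.11, with alcohol codes at 1% to 4% in both cohorts. These figures rest on assumed risks and on balance between cohorts; the dilution itself needs only that the added codes are largely unrelated to treatment choice. A reversal is possible in arithmetic but has no support in the documents. The endpoints are secondary, and the primary mortality result is not affected. The change is worth making because it is cheap.

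**What to change.** In section 9.4.2.2, for both the outpatient and the hospital version:

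1. Keep the present list as the any-substance endpoint, labelled as such.
2. Add a pre-specified comparison of F11 plus the opioid subcodes of T40, with those subcodes listed.
3. Tabulate F10, F13, F19 and the remaining T40 codes separately by cohort.
4. State that few opioid-specific events are expected in Cohort B, because its patients start opioid-naive and are censored on switching, and that the comparison is to be interpreted with this in mind.

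The cost is wording and a split of an existing code list on the same data. The opioid-specific comparison will have fewer events and wider intervals, and it adds one more secondary comparison.
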